Off-label use of descending thoracic stent graft in the ascending aorta has been described since 2003 from outside of the United States (ref #35), while Ihnken and colleagues from Stanford reported the first off-label use in the United States in 2004. (ref #36) There are a series of case reports mostly involving high-risk patients with high-risk features or pseudoaneurysms of the ascending aorta undergoing endovascular repair. (ref #37,45)

Stenting of the ascending aorta is, as reported in the literature, technically feasible but it also presents unique challenges. These include negotiating the curvature of the aortic arch, proximal fixation close to the aortic valve and coronary ostia, distal fixation that may impinge on the innominate artery, hemodynamic forces and retrograde dissection. The major complications for this procedure include perforation of the left ventricle or massive stroke. Furthermore, the ascending aorta is on the average a centimeter larger than the descending thoracic aorta, and about one fourth in length. These anatomic characteristics of the ascending aorta have ramifications in stent graft design that should entail shorter devices with large diameter for proximal and distal landing zone fixation. In addition there is a difference in variation in the maximum and minimum size of the aorta during diastole and systole. Based on 4-dimensional evaluation of our patients, we found that the variation in size is about 10% in descending thoracic aorta while it is 15% in ascending aorta. This may have ramifications in stent graft fixation for devices with poor radial force. Both the FreeFlow and the Closed Web design of the Valiant stent graft have a strong radial force to reduce endoleak rate and potential migration in the descending aorta.

In 2015, Roselli and coworkers (ref. #46) reported clinical outcomes of a 22 patient cohort with ascending pathologies treated by an endovascular approach. Clinical events reported include: 2 early conversion to open repair; 3 strokes; 2 myocardial infarctions; 2 respiratory failure, and 3 in-hospital deaths. Median follow up in this patient cohort was 12 months and actual survival at 30 days, 1 year, and 5 years was 86%, 80%, and 75% respectively.

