Pre-Enrollment Testing:	
 • Physical Exam • Vital Signs • Medical History • Pregnancy Test (if applicable) • Serum Creatinine • CTA of the chest/abdomen/pelvis, Echocardiogram.
Follow up Schedule:	
 • Discharge • 1 Month • 6 Months • 12 Months • Annually to 5 years
Centralized Image Analysis:	
Medical Data and Imaging System (M2S)
 
 • Coverage of Proximal entry tear • Aortic remodeling at 1 month, 6 month, 12 month, and annual visits up to 5 years as measured by: 
 - Change in TL size from baseline - Change in the FL Size from baseline - Change in total ascending aortic size from baseline FL Thrombosis - Continuing or new FL perfusion

Analytical Sets:	The primary endpoint analysis set will include all enrolled subjects who had at least one study scent graft implanted. The Intent-to-Treat (ITT) analysis set will include all enrolled subjects who had an intra-arterial access procedure with intent to receive the study device.
Study Monitor:	[name] Baylor Research Institute [name] [name]
Study Oversight:	A data safety monitoring committee will be used for oversight of the investigational site.

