3.3.3. Study Design

This early feasibility study is a prospective evaluation of patients receiving the device to determine the proportion in whom successful implantation is achieved, as indicated by exclusion of the thoracic lesion and graft patency at implant, time of discharge, and 1, 6, and 12 months, and annual visits through 5 years following implantation, and to determine the proportion of patients who die or experience adverse events during and after the implantation. Furthermore, the percentage of patients in whom technical and clinical success is achieved, will be determined. Additional endpoints include length of stay in intensive care unit following the procedure, and total length of hospital stay.

Twenty patients will be enrolled in this feasibility study. The enrollment will be performed in five-patient increments, and the results of each five-patient group will be analyzed and reported prior to enrolling further patients. This modus operandi serves as risk mitigating strategy.

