3.3.4.6. CT/CTA Scan

Images of the CT without contrast and CTA (contrast enhanced CT) covering the length of the lesion, which may include scans of the chest, abdomen and pelvis will be submitted for evaluation through 60 months of follow-up. Images at pre-procedure, pre-discharge, 1 month, 6 months, 12 months, 24 months, 36 months, 48 months and 60 months will be evaluated. In addition, any interim imaging done within one year of implantation should be evaluated if it relates to the performance of the implanted device. These data will be used for analysis of secondary observations at pre-discharge, 1 month, 6 months and 12 months. Site data will be used for reporting purposes at 24 months, 36 months, 48 months and 60 months, and submitted for central review.

The presence of the following endpoint related events would be assessed:

- Loss of stent graft patency
- FL diameter over the length of the stented segment
- TL diameter over the length of the stented segment
- Total aortic diameter
- FL thrombosis
- Changes in true and false lumen volumes over time
- Stent graft migration
- Presence and type of endoleaks
- Continuing or new false lumen (FL) perfusion

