3.3.5.1 Description of Endpoints

Primary endpoints will be early (at 30-days) and late death (at one-, two- and five-years), re-interventions, and surgical conversion (early or late), as well as any post-procedural stroke (early or late), ischemic or hemorrhagic events causing motoric, language or cognitive compromise.

Secondary endpoints will include access vessel complications (including dissection, thrombosis, embolization), myocardial infarction, renal failure, sepsis, pulmonary failure, blood loss over 1000cc, stent graft migration, endoleaks, technical observation (including twisting, kinking, or fracture), loss of stent graft patency (occlusion), aortic valve function (AI>2+), and any malperfusion to aortic branch-vessels (diagnosed with CTA or clinical diagnosis).

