3.3.5.3. Analysis of Endpoints

Data Analysis Sets

The primary endpoint analysis set will include all enrolled subjects who had at least one study stent graft implanted.

The Intent-to-Treat (ITT) analysis set will include all enrolled subjects who had an infra-arterial access procedure with intent to receive the study device. The primary endpoint will be reported for this analysis set as well.

Analysis of the Primary Endpoint

The primary endpoint will be analyzed using the exact binomial test method. The null hypothesis will be rejected if the upper limit of the one-sided 95% confidence interval on the 30 days mortality rate is less than 25%. The one-sided upper 95% confidence interval on the 30 days mortality rate will be calculated using the exact binomial test method.

The remainder of the primary endpoint will be presented and analyzed descriptively by reporting, for categorical variables, the number of known values and the percentage in each category, and for continuous variables, the number of known values, the mean, standard deviation (SD), median and the minimum and maximum number of subjects.

Analysis of the Secondary Observations

All secondary endpoints will be presented descriptively by reporting, for categorical variables the number of known values and the percentage in each category, and for continuous variables the number of known values, mean, standard deviation (SD), median, minimum and maximum of subjects meeting the endpoint.

Analysis of Baseline Variables

Baseline variables will be presented descriptively as described in the section above.

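### Scan-based device endpoints are summarised over known values with no rule for deaths, so on the natural reading they describe scanned survivors, not all patients who received the device

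*Combined protocol and SAP*

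**What the plan says.** The only analysis rule for these endpoints is in Section 3.3.5.3, under the secondary observations. For categorical items: "All secondary endpoints will be presented descriptively by reporting, for categorical variables the number of known values and the percentage in each category". For measured quantities it gives "for continuous variables the number of known values, mean, standard deviation (SD), median, minimum and maximum of subjects meeting the endpoint".

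The visit structure comes from other sections:

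- Section 3.3.4.6 lists the CT findings to be assessed, among them patency, migration, endoleak, lumen and aortic diameters, and "Continuing or new false lumen (FL) perfusion". It then states: "These data will be used for analysis of secondary observations at pre-discharge, 1 month, 6 months and 12 months". Scans at 24 to 60 months are also evaluated, with site data used for reporting and sent for central review.
- The synopsis (Section 3.1) lists "Aortic remodeling at 1 month, 6 month, 12 month, and annual visits up to 5 years" under centralised image analysis.
- Section 3.3.3 describes the study as a "prospective evaluation of patients receiving the device to determine the proportion in whom successful implantation is achieved", judged by lesion exclusion and graft patency at implant, at discharge and at each visit to 5 years.

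No section gives a fixed denominator for the scan endpoints, a rule for death before a scan, a composite of failure or death, a time-to-event or competing-risk summary, or any other missing-data rule. Section 3.3.4.9 deals only with withdrawal, contact attempts, and follow-up after aborted or converted procedures.

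**The concern.** The aim and the summary rule refer to different groups. The aim concerns patients who received the device. A percentage of known values at a visit concerns those alive and scanned at that visit. The difference matters because death may be related to the finding being measured: Section 3.3.4.8 itself says that early or delayed endoleak and migration may lead to rupture and death, and that twisting or kinking may lead to shock or death. A failing graft can therefore drop out of later denominators.

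Apart from 30-day mortality, every endpoint in this study is descriptive, so these tables are the evidence on device performance. With 20 patients, a handful of deaths can produce or hide a change between visits that has nothing to do with sealing or remodeling.

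**Working it through.** The documents state no expected value for any scan endpoint, so there is no planned figure to reproduce. The check compares the known-values percentage with what can be said about all implanted patients.

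**Inputs**

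- N = 20 (Sections 3.1 and 3.2.2). I assume all 20 are implanted.
- Survival S from the 22-patient ascending series in Section 2.1.1: "actual survival at 30 days, 1 year, and 5 years was 86%, 80%, and 75% respectively". As a consistency check, that series had 3 in-hospital deaths, and 19/22 = 86.4%.
- Type I endoleak of 18.6% from the systematic review in Section 2.1.1, used only to choose a plausible number of failures.
- Assumption: every survivor is scanned.

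**Formulas**

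- Deaths before the visit: d = N(1 − S), rounded. Scanned: a = N − d.
- Failures seen among those scanned: f = 0.186 × a, rounded.
- Known-values percentage: f/a.
- Share of all implanted with a failing device: from f/N (no one who died had one) to (f + d)/N (all did).
- Alive and failure-free: (a − f)/N.

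| Visit | d | a | f | Known values f/a | Range over 20 | Alive and failure-free |
|---|---|---|---|---|---|---|
| 1 month (S = 86%) | 3 | 17 | 3 | 3/17 = 17.6% | 3/20 to 6/20 = 15% to 30% | 14/20 = 70% |
| 12 months (S = 80%) | 4 | 16 | 3 | 3/16 = 18.8% | 3/20 to 7/20 = 15% to 35% | 13/20 = 65% |
| 60 months (S = 75%) | 5 | 15 | 3 | 3/15 = 20.0% | 3/20 to 8/20 = 15% to 40% | 12/20 = 60% |

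The known-values figure barely moves, while the range it leaves open widens from 15 to 25 percentage points. The separate death table cannot narrow that range, because it does not say which of the dead had failing devices.

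**Direction.** Suppose 5 of 20 devices (25%) are failing at discharge, 4 patients die by 12 months, and no failure appears or resolves. Let k of the 4 deaths be among the failing devices. The 12-month figure is (5 − k)/16, and failure or death is (9 − k)/20.

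| k | 12-month known values | Failure or death over 20 |
|---|---|---|
| 0 | 5/16 = 31.3% | 45% |
| 1 | 4/16 = 25.0% | 40% |
| 2 | 3/16 = 18.8% | 35% |
| 3 | 2/16 = 12.5% | 30% |
| 4 | 1/16 = 6.3% | 25% |

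The share that ever had a failing device is 25% in every row. The visit figure is unchanged when deaths are in proportion (k = 1), looks better when they are concentrated in failures (k = 2 to 4), and looks worse when none are (k = 0).

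**The case against.** **The denominator is unspecified rather than wrong.** Section 3.3.5.3 names neither visit nor denominator. Section 3.3.5.1 lists endoleak, migration and loss of patency beside events such as myocardial infarction and sepsis, and Section 3.3.4.8 treats uncorrected or later endoleaks as complications to be recorded. An ever/never count per subject is a possible reading, and a leak seen before death would then stay counted. This stands in part: the survivor denominator is an inference. But Section 3.3.4.6 ties the scan analysis to fixed visits, and an ever/never count cannot serve patency, lumen size or false-lumen perfusion over time. Whichever reading is meant has to be written down.

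**The direction is not established.** A reader might infer that the plan makes the device look better as the worst cases die. The documents do not support that as a general statement. The systematic review in Section 2.1.1 gives 15.2% all-cause but only 5% aorta-related mortality, so (15.2 − 5)/15.2, about two-thirds, of those deaths were not aorta-related, and this trial enrols ASA IV patients. Assuming very high mortality among patients with a leak would give a large bias, but no such rate is cited.

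**Scope.** False-lumen perfusion and remodeling are absent from the secondary list in Section 3.3.5.1, and scans after 12 months are for reporting. That is correct. Their data nonetheless feed the secondary observations through Section 3.3.4.6, and no other summary rule exists for them.

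**Safeguards.** The number of known values is shown, death is a primary endpoint, autopsies are requested, interim imaging in the first year is evaluated, and results are analysed after every five patients. These make a shrinking denominator visible. They do not separate death from a missed scan or show the last device status in the tables.

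**Proportion.** This is an early feasibility study and no secondary endpoint carries a decision rule. That limits the weight of the point but does not remove it.

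**Conclusion.** The point holds as a mismatch between the question and the summary. On its natural reading the plan reports scan findings in survivors, whereas Section 3.3.3 asks about all patients receiving the device, and no other section closes the gap. At 12 months in the illustration, a reported 18.8% is compatible with anything from 15% to 35% of implanted patients having a failing device, with 65% alive and leak-free. This rests on 20 implants, survival as in the cited series, all survivors scanned, and an illustrative three leaks.

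The effect on endoleak and migration has no fixed sign. A reader might also take 1/S − 1, that is 16%, 25% and 33% at 30 days, 1 year and 5 years, as the amount by which successful repair is overstated. That is the cited mortality re-expressed under the assumption that every survivor is a success. It contains no scan information and should not be quoted as imaging bias.

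The 30-day mortality test in Section 3.3.5.3 is unaffected. The change is worth making because it is cheap and answers the stated aim.

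**What to change.** In Section 3.3.5.3, under the secondary observations:

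1. At each visit, report each categorical scan endpoint over all implanted subjects due for that visit, in four categories: success; failure; died before the scan (with the last scan finding); alive but not scanned. Keep the percentage among scanned survivors beside it.
2. For endoleak, migration and loss of patency, also report the cumulative number and proportion of implanted subjects with a first event, with death as a competing event, so that an event seen before death stays counted. If follow-up is complete this is simply the number of subjects with a first event divided by the number implanted.
3. Label mean changes in true-lumen, false-lumen and total aortic size as applying to survivors with a scan, and give the number who have died.

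The cost is a few sentences and one extra table, using data already collected. The all-implanted success figures will look less favourable and will include deaths unrelated to the graft, which is why the survivor figure should stay alongside.

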3.4 Potential Risks and Benefits

3.4.1 Potential Risks

Treatment with the Medtronic Thoracic Stent Graft System is an invasive procedure that poses significant risks to the patient. Patients participating in this trial as study patients will be exposed to such risks. These risks include:

Likely

- Bleeding during and/or after the procedure;
- Problems at the groin sites where the catheters are inserted including after the procedure are done which include:
 - Bleeding
 - Delayed wound healing
 - Wound separation
 - Wound drainage
 - Nerve injury, damage, irritation and / or pain
 - Wound infection in 1 or both groins or deep in the tissue where the catheter was placed
 - Pain caused by the implant procedure

Less likely

- New onset of pain or worsening of existing pain in buttocks and / or legs;
- Swelling of legs

Rare but serious

- Problems with blood's ability to clot;
- Injury to the blood vessel wall including separation of layers of the vessel wall;
- Tearing or rupture of the blood vessel;
- Breaking apart of plaque within the blood vessel;
- Injury to the heart and/or heart valve;
- Irritation within the blood vessel;
- Transfusion reaction
- Allergic reaction from the contrast, medication(s) and/or stent graft material; Narrowing of the blood vessel;
- Rupture of the aneurysm/dissection;
- Partial rupture of the aneurysm/dissection;
- Aneurysm/dissection expansion or pseudoaneurysm;
- Local collection of blood or fluid under the skin causing swelling and/or discoloration;
- Movement of the stent from its original site; Blockage of blood flow through the stent-graft;
- Blockage of blood flow through a blood vessel near the aneurysm;
- The polyester graft material may break open;
- Failure to deliver the stent-graft to correct location;
- Stent deformity;
- The stent graft may twist or kink
- The stent graft may fail to open;
- The balloon used to smooth the stent graft may break;
- Re-narrowing of the blood vessel;
- Temporary narrowing of the blood vessel;
- Ongoing leaking of blood through the graft material into the aneurysm;
- Ongoing leaking of blood into the aneurysm from one or more small vessels near the aneurysm;
- Kidney failure or insufficiency;
- Blood clots in the kidneys;
- Pneumonia and breathing problems such as lung congestion;
- Blood clots in the lungs;
- Failure of lungs to take in enough oxygen;
- Irregular heart beat;
- Chest discomfort or pain;
- Heart attack or fluid around the heart;
- Congestive heart failure (failure of the heart to adequately pump blood with resulting back-up of fluid in the veins);
- Catheter breakage;
- Breakage of the metal stent that could possibly cause a leak and may result in aneurysm growth and or rupture;
- Reaction to the medications or anesthesia;

- Decreased blood flow to the intestines;
- Bowel ischemia (temporary or permanent lack of blood flow to the intestines causing them to stop working); blockage of the bowel or death of the bowel;
- Impotence (inability of a male to have or maintain an erection);
- Nerve damage;
- Inability to tolerate food;
- Urinary tract infection;
- Infection of the stent graft causing fever;
- Staying in the hospital longer than 4 days;
- Surgery may be needed should something go wrong during the procedure;
- Failure of vital organs to function;
- Decreased blood flow to the spinal cord causing permanent or temporary paralysis (inability to move/use legs) with possible inability to control bowel and bladder function;
- Change in brain function that may cause temporary weakness and/or awareness;
- Stroke from bleeding or from a clot that forms in the brain;
- Radiation injury or injury to cell life due to therapeutic radiation;
- Death

Reproductive Risks:

Because the drugs in this study could harm an unborn baby, patients should not become pregnant while on this study. Patients should not nurse a baby while in this study.

Radiation Risks:

The following procedures completed throughout the study pose as a radiation risk to patients participating in the study:

- CT Scan of your chest, abdomen and pelvis with and without contrast
- Angiogram (x-ray) of your aorta and the arteries
- Fluoroscopy and/or Intravascular Ultrasound/IVUS (x-rays taken from inside the arteries)
- CT scan of your chest after the procedure

These risks include the potential for discomfort or complications resulting from the procedure, the implanted stent-graft as well as the patients overall participation in the study as described in Section 3.2 and 4.8.

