In 2016, Zhenjiang et al (ref. #47) reported clinical outcomes of a 15 patient cohort that underwent endovascular repair for ascending aortic dissections. Technical success was achieved in all patients with no major morbidity or deaths perioperatively. Clinical events reported include: 1 retrograde aortic dissection, 1 cardiovascular ischemia, and 1 supraventricular tachycardia. Other morbidities included perigraft endoleak, a bird-beak sign, a temporary pericardial effusion, and a left kidney atrophy. Significant enlargements of true lumens and shrinkage of false lumens and overall thoracic aorta were observed at 12 months.

In 2018, Muetterties and coworkers (ref. #48) conducted a systematic review of 46 publications regarding primary endovascular repair of the ascending aorta with 118 total patients. The most commonly treated aortic disease was type A aortic dissection (50%). Clinical events reported included: type I endoleak (18.6%), all-cause mortality (15.2%), aorta-related mortality (5%), conversion to open surgery (3.4%), and cerebrovascular complications (3.4%) with an average follow-up of 17.2 months.

In 2016, Tsilimparis and coworkers (ref. #49) retrospectively reviewed 10 patients who received the Zenith Ascend TAA Endovascular Graft for treatment of disease pathologies of the ascending aorta. All endografts were successfully deployed without intraoperative adverse events at the targeted landing zone. Clinical success in coverage of the lesions was achieved in all cases with the exception of an attempted treatment of an intraprocedural aortic valve implantation dissection that resulted in early mortality. Clinical events reported include: 1 stroke with paraplegia, 1 transient ischemic attack, 1 early evacuation of a hemopericardium, and 2 late interventions for persisting endoleaks. 30-day survival was 90%. At a mean follow-up of 10 months, three late deaths occurred, with one treatment related, as a result of graft infection.

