In addition, an article was published in 2016 (ref. #50) evaluating the Valiant PS-IDE stent graft under investigation in the IDE protocol. Khonyezhad et al prospectively enrolled 6 patients at their single site and reported no early mortality and 1 late death. Other clinical events include: 1 type 1a endoleak, 1 post-operative stroke, and regression of the aortic lesions in the excluded aortic segment. There is positive remodeling of the aorta and uniform accuracy of deployment with secure fixation up to 17.5 months of follow-up.

Collectively, these studies report early outcomes following ascending endovascular treatment in patients deemed high surgical risk comparable to open repair in lower risk patients. Open surgical repair of acute Type A dissections, current gold standard treatment, is an invasive procedure with average 85% early (30-day) survival (ref 4-7). Due to invasiveness and influence of patient risk factors on outcomes, open repair is offered only to select patients. Patients deemed extreme high-risk or non-surgical candidates due to co-morbidities are routinely medically managed and the natural history of Type A dissection is poor with 50% survival in the first month if no surgery is offered (ref #11,12).

These findings lend support to the feasibility and potential life-saving benefit of endovascular intervention of ascending pathologies in patients deemed high open surgical risk with appropriate anatomy (the target population of the IDE). These articles also highlight the challenges of endovascular treatment in the ascending aorta, including the lack of devices designed for ascending use, anatomical complexity and patient selection. The intent of this IDE is to further evaluate the Medtronic Thoracic Stent Graft System as an endovascular treatment option in patients deemed high open surgical risk with appropriate anatomy.

2.1.2 Bibliography of Publications Relevant to Evaluation of Safety and Effectiveness of the Device

References Cited

2. Acierno L. *The History of Cardiology*. New York, NY, Parthenon Publishing Group, 1994.
3. Daily PO, Trueblood 11W, et al. Management of acute aortic dissections. *Ann Thorac Surg* 1970;10:237-47.

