3.3.4.8. Adverse Events

Any adverse experiences reported by a subject in the study or noted by the Clinical Investigator/Sponsor, will be reported on the Post-Operative Assessment CRF. Each experience must be categorized by the Clinical Investigator/Sponsor by its degree of severity (mild - the event did not require treatment, moderate - the event was treated locally or by minimally invasive treatment, or severe - the event was fatal or resulted in permanent injury or disability), its relationship to study device and implantation procedure (not related, associated with, caused by), and whether or not the adverse experience was unanticipated. An unanticipated adverse effect as defined by the FDA is any serious adverse effect on the health and safety or any life-threatening problem or death caused by, or associated with, a device, if that effect, problem or death was not previously identified in nature, severity or degree of incidence in the investigational plan or application (including a

supplementary plan or application), or any other unanticipated serious problem associated with a device that relates to the rights, safety or welfare of subjects (Section 812.3). Refer to Appendix 2, Instructions for Use and the Study Subject Informed Consent (Appendix 4) for a listing of known events.

Adverse events are to be scored as follows:

0 = None; the event was not observed

1 = Mild; the event was observed, but no treatment was required or the event resolved without treatment

2 = Moderate; the event was treated locally or by minimally invasive means

3 = Severe/Serious; as defined below

All events scored as "3" or "severe" are considered serious adverse events (SAES) under the regulatory definition in 21 CFR 803. These events will be reported within five working days to FDA. Specifically, serious illness or injury is one that is:

- Life-threatening (or fatal),
- Results in permanent impairment of a body function or permanent damage to a body structure; or
- Necessitates medical or surgical intervention to preclude permanent impairment of a body function or permanent damage to a body structure.

The Clinical Investigator/Sponsor will report all unanticipated, device deterioration events to the FDA.

Historical data have demonstrated that several types of complications are known to occur with this procedure. These complications are described in the following sections.

Endoleaks

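### Section 3.4.1 classes death, stroke and need for surgery as rare, against about 3% to 17% in most of the plan's own ascending-aorta evidence, and omits type I endoleak

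*Combined protocol and SAP*

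**What the plan says.** Section 3.4.1 (Potential Risks) has three tiers: likely, less likely, and "Rare but serious". None has a numeric definition. The third tier includes "Stroke from bleeding or from a clot that forms in the brain", heart attack, inadequate oxygen uptake by the lungs, and surgery if the procedure goes wrong. Death is its last item, directly after "Radiation injury or injury to cell life due to therapeutic radiation". The leaks it names are through the graft fabric, from small branch vessels, or possibly after stent breakage. Attachment-site leak, which Table 2 in section 3.3.4.8 calls type I, is not on the list.

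Section 2.1.1 (Background) reports outcomes in comparable patients. For the 22-patient ascending series it gives "3 strokes; 2 myocardial infarctions; 2 respiratory failure, and 3 in-hospital deaths", plus 2 early conversions. For the 6-patient series of the first-generation study device it says "Other clinical events include: 1 type 1a endoleak, 1 post-operative stroke". It also cites a 118-patient review, ascending series of 10 and 15 patients, an arch series and a mixed-location registry.

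Section 3.3.4.8 treats a serious device-associated event as unanticipated if it was "not previously identified in nature, severity or degree of incidence in the investigational plan" or in the application. For known events it says: "Refer to Appendix 2, Instructions for Use and the Study Subject Informed Consent (Appendix 4) for a listing of known events". Section 7 sends unanticipated events to the IRB and FDA within 10 days, and leaves other adverse events to the IRB continuing review and the FDA annual review. Sections 3.3.4.8 and 3.4.2.1 (item 8) send every severe event to FDA within five working days.

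**The concern.** One document gives two incompatible pictures of the same risks. The tier label says death, stroke and conversion are rare, while the evidence offered to justify the study shows them in several per cent of patients or more.

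Two uses of the text are affected. First, 3.4.1 is the plan's formal statement of risk, on which an IRB would rely when judging patient information. Second, the unanticipated-event definition depends partly on incidence already identified in the plan. The plan has no table of expected incidence. It has an undefined label and a set of literature rates that disagree with it. Under section 7 this classification separates prompt IRB notice from continuing review. Two careful readers could classify the same device-related stroke differently.

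**Working it through.** **1. Reproduce the plan's own figure.** The 22-patient series had 3 in-hospital deaths, and 1 − 3/22 = 86.4%, which agrees with the 86% 30-day survival in 2.1.1. The review's percentages match 22, 18 and 4 of 118 (18.6%, 15.25%, 3.4%). The arch series' percentages match 2 and 6 of 58 (3.4%, 10.3%). Those counts are inferred from the percentages.

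**2. Rates from section 2.1.1.** Rate = x/n. Brackets hold exact (Clopper-Pearson) 95% intervals: the lower limit is the 2.5% quantile of Beta(x, n−x+1) and the upper is the 97.5% quantile of Beta(x+1, n−x).

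| Source | Death | Stroke | Conversion | Type I endoleak |
|---|---|---|---|---|
| Ascending, n=22 | 3 in hospital, 13.6% (2.9–34.9) | 3, 13.6% (2.9–34.9) | 2, 9.1% (1.1–29.2) | not given |
| Ascending dissection, n=15 | 0 perioperative (0–21.8) | none reported | none reported | type not stated |
| Ascending, n=10 | 1 at 30 days, 10% (0.3–44.5) | 1, 10% (0.3–44.5) | not given | type not stated |
| First-generation device, n=6 | 0 early (0–45.9); 1 late | 1, 16.7% (0.4–64.1) | not given | 1, 16.7% (0.4–64.1) |
| Review, n=118, mean follow-up 17.2 months | 15.2% over follow-up (9.3–23.0) | 3.4% cerebrovascular (0.9–8.5) | 3.4% (0.9–8.5) | 18.6% (12.1–26.9) |
| Arch, n=58 | 3.4% at 30 days (0.4–11.9) | 10.3% (3.9–21.2) | not given | not given |
| Mixed-location registry, n=304 | 7.2% at 1 month | 1.6% | not given | not given |

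Myocardial infarction and respiratory failure were 2/22 each (9.1%, 1.1–29.2), in one series only.

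**3. Crude pooling of the four small ascending series** (22 + 15 + 10 + 6 = 53):
- Early death: (3 + 0 + 1 + 0)/53 = 7.5% (2.1–18.2).
- Stroke: (3 + 0 + 1 + 1)/53 = 9.4% (3.1–20.7), assuming none in the 15-patient series. Without that series it is 5/38 = 13.2% (4.4–28.1).

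The review is left out because the documents do not say whether it overlaps these series.

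**4. What the label implies for 20 patients.** P(at least one) = 1 − (1 − p)^20. The plan gives no figure for rare, so 0.1% and 1% are assumptions.

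| p | P(at least one in 20) | Expected number, 20p |
|---|---|---|
| 0.1% (assumed) | 2% | 0.02 |
| 1% (assumed) | 18% | 0.2 |
| 1.6% (lowest cited non-zero stroke rate) | 28% | 0.32 |
| 3.4% | 50% | 0.68 |
| 10% | 88% | 2.0 |
| 13.6% | 95% | 2.72 |

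**5. The mortality criterion.** Section 3.3.5.3 requires the exact one-sided 95% upper limit for 30-day mortality to be below 25%. With 20 patients the limit is 13.9% for 0 deaths, 21.6% for 1 and 28.3% for 2. The plan thus measures 30-day death against a quarter of patients. This is a rejection threshold and not an expected rate, so it supports the point only as context.

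**6. The incidence reference.** The definition in 3.3.4.8 compares an event with the whole plan or application. That includes both the label in 3.4.1 and the rates in 2.1.1, and nothing says which governs.

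**The case against.** Rare has no number attached, and the same tier holds urinary infection and a hospital stay over four days. It can be read as a catch-all rather than an estimate. The section opens by acknowledging significant risks. The series are small and mix pathologies and time points, and some are reassuring: 0/15 and 0/6 early deaths, 3.4% and 7.2% 30-day death in the arch and registry series, and 1.6% stroke in the registry. This stands as a limit on precision. It does not rescue the label, because a tier named rare beside two more frequent tiers does state a frequency.

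Four stronger readings are tempting, and the documents do not support them:

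- *Endoleak is wrongly called rare.* The 18.6% is for type I, which 3.4.1 does not list. The defect is omission, and type I is covered in Table 2 and, as landing-zone leak, in 3.4.2.2.
- *Patients are misinformed.* The consent form is not in the reviewed text. Wording addressed to the patient in 3.4.1 hints at shared text, but that is inference. Section 3.4.2.1 requires the endovascular, open and medical options to be explained.
- *The unanticipated-event rule has a false reference or cannot work.* Its reference includes the rates in 2.1.1, so it is inconsistent rather than false.
- *No cluster of events could trigger a report.* Severe events go to FDA within five working days whether anticipated or not, each five-patient group is analysed and reported before further enrolment, and a DSMB reviews adverse events periodically. Section 7 read alone appears to send other events to annual review. That is a separate conflict.

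Nor does every source contradict the label for death, given the two series with no early deaths.

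**Conclusion.** The point holds for death, stroke and conversion. In the four small ascending series, early death ranges from 0 to 13.6%, and reported stroke from none to 16.7%. Conversion is 9.1% in one series and 3.4% in the review. All-cause death of 15.2% in the review is over an average of 17.2 months and is not an early rate. Type I endoleak (18.6% and 1/6) is a separate omission from the list.

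The consequence is limited to the risk statement and to classification of serious device-associated events, which matters mainly for the timing of IRB notice. No endpoint, sample size or analysis changes.

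The conclusion assumes that rare means about 1% or less, and that the cited ascending series are relevant to this trial, as section 2.1.1 itself argues. It does not assume that the trial's rates will equal theirs. The case for myocardial infarction and respiratory failure is weaker.

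**What to change.** - Take death, stroke and surgical conversion out of the rare tier in 3.4.1. Reconsider myocardial infarction and respiratory failure, noting that 3.4.2.2 (item 14) also calls the latter rare.
- For these events, replace the tier label with a table giving event, time point, numerator, series size and source from 2.1.1. Keep early and follow-up figures apart.
- Include the low results: 0/15 and 0/6 early deaths, 3.4% and 7.2% 30-day death, and 1.6% stroke. A stroke range drawn from all of 2.1.1 should start no higher than 1.6%, and the 15-patient series without major perioperative morbidity should be shown.
- Add type I endoleak to the list, with 18.6% and 1/6.
- In 3.3.4.8, name this table as the reference for expected incidence.
- Check that the consent form agrees with it.
- As a clerical item, correct the appendix pointers in 3.3.4.8. The contents list shows Appendix 2 as a right-of-reference letter, Appendix 4 as the case report forms and Appendix 5 as the consent form. Section 3.3.4.2 places the instructions for the current device in Appendix 14.

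The cost is a wording amendment, including the consent form if it differs, and a less favourable stated risk. No new data are needed.
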